Study staff will assess participants for any medical or psychiatric side effects by asking the participant "How have you been feeling since I saw you last?" Study staff will also review the previous AE form and inquire whether any of those events are continuing. Study clinicians will follow all AEs, regardless of severity, until resolution or until four weeks following completion of the trial. Each new or unresolved AE will be recorded on the AE case report form according to standard procedures. All AEs will be assigned a severity (mild, moderate, severe or life-threatening), as defined by the DAIDS Table for Grading Severity of Adult Adverse Experiences for HIV Prevention Trials.¹⁴⁸ The study clinician will review the information and offer an educated opinion about the relatedness of the event to the study drug. These data will be reviewed by the PI or Co-Investigator on a weekly basis.

A summary report of all AEs (including SAEs) will be prepared at least every six months (frequency determined by our IRB, DSMB, and NIH), to be submitted to the DSMB, IRB and NIH. SAEs are defined as any fatal event, any immediately life-threatening event, any permanent or substantially disabling event, any event that requires or prolongs inpatient hospitalization, or any congenital anomaly. This category also includes any other important medical event that a study investigator judges to be serious because it may jeopardize the subject or require intervention to prevent one of the above reportable outcomes, or which would suggest a significant hazard, contraindication, side effect, or precaution. An unexpected event is one that is not described with respect to nature, severity, or frequency in the current protocol, investigator's brochure, or product labeling. All AEs that are both serious and unexpected will be reported to the DSMB and UCSF IRB, in writing, within 10 working days. If the SAE is fatal or life threatening, the PI will notify the FDA by telephone within 24 hours, with a followup written report within two working days.

As required, expedited reporting of SAEs to the NIH will adhere to the following guidelines:

1. Apply regardless of the investigator's assessment of the relatedness of the SAE to the intervention under study;
2. Apply equally to trials requiring an IND and those not requiring an IND;
3. Apply to any SAEs that occur during the post-treatment observation period defined by the protocol; and
4. Apply to suicidal or homicidal behavior that causes an SAE in the participant or someone else (e.g., hospitalization or death).

SAE reporting will include a narrative that will provide details of relevant screening measures, medical history and physical findings, treatment compliance, participant reports of SAEs, and any other required information. The completed SAE report will contain: subject's ID, gender, age, the title and date of the SAE, and narrative explanation. The SAE form will track how the research staff was notified of the event, dates of consent, randomization, study screening for inclusion/exclusion, treatment received, outcome of study treatment, dates and circumstances of the hospitalization/death, whether alcohol or drugs were known to be involved, and participant status at last clinical or research contact. In cases of participant death, the report will also include appropriate substantiation from clinic records, and, whenever

possible, copies of the death certificate, autopsy report, or medical record. As Medical Monitor for the study, [name], will state whether the event was expected and assess its relatedness to the study medication or intervention.

Reporting of other study events. As the study is being conducted, [name] (PI) will inform the NIH, IRB, and DSMB of any changes in recruitment or in the protocol that are relevant to safety, as well as any actions taken by the IRB as a result of its continuing review of the study. In the event of any major changes in the status of an ongoing protocol (which will occur only with IRB approval), the contact PI will inform the NIH's program officer and the DSMB immediately. Such changes would include, but are not limited to: amendments to the protocol; temporary suspension of patient accrual, or of the protocol; any change in informed consent or IRB approval status; termination of patient accrual or of the protocol; or other problems or issues that could affect the human subjects in the study.

Trial stopping rules: There are no formal trial stopping rules for this study. No formal interim efficacy analysis will be conducted. If it becomes clear that the trial puts undue safety risk on study participants, outcomes are poor, or the trial will not achieve its enrollment goals, consideration will be given to stopping the trial, after consultation with the DSMB, IRB, and NIDA PO. The overall safety risk to study participants will be determined through regular monitoring procedures. Safety issues will be evaluated as they arise; participants are given the pager number of the clinician on call which they can page in the event of an emergency or safety risk. Study clinicians will consult with [name], the Principal Investigator and [name], the medical director, on these safety issues on a case-by-case basis as they are reported by the participant. Non-urgent clinical issues that arise during the course of the study are discussed by the team's research clinicians at the next weekly meeting with the PI [name]. During weekly meetings, study clinicians will review all the safety issues and incident adverse events (including lab abnormalities) for the study overall, by system category, and by possible relationship to the study drug. The PI will alert the DSMB and the NIDA PO immediately if at any point the team observes an unexpected frequency of serious AEs possibly related to kudzu. At that point, the PI will consult with the DSMB to determine if changes to the protocol or consent form are needed, or if additional safety data are needed to evaluate participant safety. The PI will consult the DSMB to determine if the trial should be stopped after the committee has reviewed available safety data to date.

14.2 * DATA AND SAFETY MONITORING BOARD (DSMB): (REQUIRED) Will a Data and Safety Monitoring Board (DSMB) be established:

Yes
 No

14.3 DSMB DETAILS: Provide details about the DSMB, including meeting frequency, and the affiliations and qualifications of members: **Attach the DSMB charter to the Other Study Documents section. If the DSMB has not yet been established, submit details and the charter to us as soon as they become available.**

The research team has used the UCLA Data Safety Monitoring Board (DSMB) for Addiction Medicine, of which [name] is currently a member, for past clinical trials; we will do so for this trial as well. The purpose of the DSMB is to monitor participants' progress in trials in order to identify emerging and unexpected events that change the known risks to subjects' participation. The UCLA DSMB reviews multiple studies in separate review committees. It has a project director who assigns committee reviewers to review studies. The reviewers remain anonymous to the PI and the coordinator communicates the concerns of the committee to the PI. When the PI responds to the concerns raised by the committee, they also send them through the coordinator who then passes it to the committee. The PIs are never part of, nor sit in the committee that reviews their own study.

The DSMB will be given blinded trial data, but may request unblinding if safety data warrant. The DSMB clinicians will review reported AEs that are identified by study clinicians or other staff members who evaluate the subjects. The statistician will review the data periodically to monitor problems that emerge from AE occurrences as well as subjects' self-report instruments that query about psychological and physical complaints. The safety monitoring process begins with the initial DSMB review and approval of the protocol. This review is conducted at multiple levels, including not only the DSMB, but also the NIH and the UCSF IRB. For this study, the DSMB will meet six months into the trial or earlier if warranted, and then annually and on an as-needed basis. The DSMB will review the data collected during this trial to provide ongoing information to [name], to the IRB, to the NIH, and potentially (if clinically warranted) to subjects about changes in the risks and benefits from research participation. Communication between the DSMB and the study site will be forwarded to the UCSF IRB and the NIH, for consideration as to whether there are changes to risks and benefits, or if any unexpected events have occurred (see DSMBAM info sheet in other study documents).

Below are members who serve as committee chairs as well as clinical research experts:

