Study medication: The Safeway Compounding Pharmacy, which currently prepares our study drug for our ongoing clinical trials, will provide the study drug kits for the proposed trial. Drugs are over-capsuled in a locking capsule to ensure the same appearance across all study arms and maintain double-blind. Study medications will be dispensed by the study clinician in MEMS® capped bottles with dosing instructions, date of dispensing, prescribing clinician, a 24-hour telephone study phone number for medical emergencies [contact]), and advisements against drug combinations. **Training on targeted dosing:** Participants will be trained on targeted medication dosing during enrollment and be provided an instructional leaflet for reference. They will be instructed to take 1 tablet when they believe that meth use risk is high or when meth use is imminent.¹⁰⁹ Participants will be given seven 50mg tablets per week and will be instructed to not exceed 1 tablet every 24 hours.¹⁰⁹ Based on concordance in adherence measures (self-report, pill count, and electronic monitoring) in our *double-blind* trials, we are confident that very little, if any, sharing of study medications is occurring between *blinded* participants.^{168,169} As a precaution, participants will be briefed about the importance of not sharing medications.

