EMA and EMI procedures: The EMA and EMI platform will be programmed and administered using the HIPAA-compliant platform of PiLR Health (MEI Research), which is capable of deploying text messaging prompts that pull and push content to participants that are timed, randomized, and triggered by specific logic and skip programs based on real-time data. Hence, this platform can be tailored to suit the needs of the study to collect EMA data and administer EMA-informed EMI adherence reminders. We already utilize PiLR Health' platform to develop and implement automated surveys and dynamic prompts on our ongoing studies. For this study, participants in both arms will receive EMA surveys for data collection using established methods consistent with EMA protocols that involve daily assessments at set and random time periods.^{112,114,115} Consistent with our other studies, EMA surveys will capture data on the drug use antecedents (craving, mood, and stress) previously shown to predict drug use in the literature and our prior research^{116,118,172-176}; data on recent meth use^{112,116,118}; and data on study drug use¹¹⁶ (**Table 3**). Each day, participants will receive a series of up to five EMA surveys that monitor these constructs near real-time (note: the number of random surveys may be adjusted based on the findings on the number of questions threshold of acceptability from the cognitive interviews). One survey will be consistently deployed during the time when the participant begins their day; up to four additional surveys will be deployed at random times throughout the same day.^{112,114,115} Participants will also receive additional prompts to take their medication during days when they have not yet taken their study medication, but have reported high levels of craving, stress, or bad mood (i.e., EMA-informed EMI adherence reminders). Participants will receive stipends for completing the EMA surveys and the stipends will be escalated over follow-up to maintain engagement and response rate. In final ACASI surveys, we will assess the acceptability of lowered or no stipends for the EMA surveys, as well as alternative incentives that have been deemed acceptable in other clinical settings (e.g., raffle drawings¹⁷⁷, ultra-low magnitude reinforcers¹⁷⁸).

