HIV and STI Testing risks. Participants may experience anxiety surrounding HIV testing results, regardless of the outcome. Positive results in particular may be stigmatizing, emotionally upsetting, and cause psychological distress. Testing will be done by a trained counselor and will include education on the meaning of results, risk-reduction counseling, and referral for treatment. Due to mandated reporting requirements, there could be a loss to confidentiality if there is a new case of HIV.

Naltrexone, Opiates and Fentanyl Risk: Naltrexone is a medication that blocks your body's ability to respond to opiate medicines or drugs, such as Oxycontin, methadone, or heroin. If you have taken opiates 7-10 days prior to taking naltrexone, there is a risk of mild to severe opiate withdrawal symptoms. If you take opiate medications for pain or are dependent on opiates for any reason. We have included a list of opioid medications in other study documents. If you are receiving naltrexone instead of placebo, you may not feel pain relief from opiate medications for 24 to 72 hours. This blocking effect can be overcome, but it must be done by an experienced physician, usually in the emergency room or hospital. If you take large amounts of opiates, including opiate-containing medications such as prescription pain pills (a guide will be given with

common names of opiate medications) or heroin, this can lead to overdose, including coma or death.

On the streets, dealers are mixing fentanyl with other drugs, such as heroin, cocaine, methamphetamine, and MDMA. Because fentanyl is cheap and very powerful, adding it to other drugs can be more profitable for dealers. This is especially risky when people taking drugs don't realize that fentanyl might be present in their drug supply. Fentanyl is known by such names as Actiq®, Duragesic®, and Sublimaze®. Street names for illegally used fentanyl include Apache, Dance Fever, Friend, Goodfellas, Jackpot, Murder 8, and Tango & Cash.

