Minimizing the risks of medication side effects. At all times, participants will be encouraged to contact the study clinician if they have questions or concerns about their medication dosage. During each study visit, participants are given the opportunity to discuss any adverse medication effects with the study clinician. Participants will have monthly safety blood tests, including liver function tests, during the 12 weeks they are taking study drug. Participants who ultimately do not tolerate their medication may be

taken of study medication if needed and will continue to be followed throughout the duration of the trial.

We will be testing potential participants for opiates, other substances and fentanyl during screening since naltrexone can cause opioid withdrawl. Participants who test positive for opiates or fentanyl will not be enrolled in the study. We will also test participants for opiates, other substances and fentanyl during monthly in-office safety visits and any positive results will not be given naltrexone.

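### The EMI trigger in 8.9 has no term for study-drug status, so as written it would still prompt participants whom 13.3 has taken off, or denied, study drug

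*Protocol*

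**What the plan says.** Section 13.3 (Minimizing Risks) describes two ways of being off study drug after randomization.

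- **Positive test.** Opiate and fentanyl testing is repeated "during monthly in-office safety visits and any positive results will not be given naltrexone". The text does not say how long drug is withheld, whether dispensed tablets are affected, or whether these participants remain in follow-up.
- **Intolerance.** Participants who cannot tolerate the medication may be "taken of study medication if needed and will continue to be followed throughout the duration of the trial". Removal is discretionary; continued follow-up is explicit.

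Section 8.9 (EMA and EMI procedures) gives both arms an automated platform whose messages can be "triggered by specific logic and skip programs based on real-time data". The reminder rule is: "Participants will also receive additional prompts to take their medication during days when they have not yet taken their study medication", when they have also reported high craving, stress or bad mood. No other condition is named.

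Section 8.9 (Study medication) sets an as-needed regimen with a full daily supply: "Participants will be given seven 50mg tablets per week and will be instructed to not exceed 1 tablet every 24 hours". Pill counts (8.9, Study drug adherence) serve to measure adherence. No section describes taking tablets back or switching the reminders off.

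**The concern.** The purpose of the opioid testing is clear from section 13.2, which warns that for someone with recent opiate use "there is a risk of mild to severe opiate withdrawal symptoms" when naltrexone is taken. The reminders are not neutral notices: 8.9 (cognitive interviewing) tests whether they convey the benefit of dosing at that moment and give a clear cue to do so. If the trigger runs unchanged, the trial's own automated intervention encourages dosing in people for whom 13.3 has withheld the drug on safety grounds, and in those taken off it because they could not tolerate it.

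There is a smaller effect on the data. Table 4 (8.11) records receipt of EMI prompts daily, and the exploratory analysis in 8.13 relates EMA responses, prompts and pill-taking to one another, then asks whether the efficiency of that pathway moderates the treatment effect. An off-drug day with a prompt and no pill would look like a failure to respond, although no response was wanted.

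**Working it through.** The plan gives no figure on this point to reproduce. The check sets the rules side by side and counts days.

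**1. Does the trigger depend on study-drug status?** It has two parts: (a) no study drug taken yet that day; (b) high craving, stress or bad mood reported. A participant who is off drug and complies with that meets (a) every day. The trigger then reduces to (b), and any qualifying report produces a prompt.

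**2. Does such a participant still receive EMA surveys?** For intolerant participants, 13.3 states continued follow-up, although it does not mention EMA or EMI by name. For opioid or fentanyl positives it is an inference, from the intention-to-treat principle in 8.13 and the SAP and from the absence of any rule withdrawing them.

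**3. For how long could prompts fire?** Inputs: EMA runs through the 12-week treatment period (8.9, compensation), so 12 × 7 = 84 days. Post-enrollment opioid and fentanyl tests fall at weeks 4, 8 and 12 (8.9, Opioid and Fentanyl testing). Days remaining = 84 − 7 × (week of test).

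| Positive at | Calculation | Days remaining |
|---|---|---|
| Week 4 | 84 − 28 | 56 |
| Week 8 | 84 − 56 | 28 |
| Week 12 | 84 − 84 | 0 |

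These are upper bounds. They assume that withholding lasts to the end of treatment, and prompts fire only on days with a qualifying report. If a week-4 positive were given drug again at week 8, the figure would be 56 − 28 = 28 days. For intolerance the range is 0 to 84 days, depending on when drug stops.

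**4. Could the participant hold tablets?** Supply is seven a week, taken as needed, so leftovers are possible. With weekly dispensing and no carry-over the range is 0 to 7. If four weeks' supply were handed over at each in-office visit it would be 0 to 4 × 7 = 28. The second case is an assumption: nine of the 12 weekly visits are remote (13.4), and how drug reaches participants then is not stated. Carry-over from earlier weeks would raise both upper limits.

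**5. Reading used.** The sentence in 13.3 on monthly testing also lists other substances. It is read here as applying to opiates and fentanyl, in line with the enrollment rule just before it. It names naltrexone, but in a double-blind trial it is taken to apply to study drug in both arms.

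**The case against.** The best defence is that this is silence and not contradiction. Section 8.9 describes reminders for people using their study medication, 13.3 describes withholding, and neither says that prompts go on afterwards. The platform can be tailored, so staff may well switch reminders off in practice. That stands in part: nothing shows that prompts will in fact continue. But 8.9 states a trigger, and that trigger applied as written would fire. The gap lies in the stated rule.

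Safeguards also exist. Participants are reminded weekly that naltrexone interacts with opioids and receive a guide to opioid-containing drugs (8.9, Opioid and Fentanyl testing); bottles carry advice against drug combinations and a 24-hour number (8.9, Study medication). Clinicians review data forms daily (13.3) and safety weekly (14.1). Current opioid use and an opioid-positive screen or enrollment test are exclusions (11.8), which should keep numbers down. And 20 of the 60 participants receive placebo (11.1), which cannot precipitate withdrawal. All of this lowers the risk; none of it changes the trigger.

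A reader might go further and infer that most positives will be holding a sizeable stock. For example, the pilot's 64% dosing on high-risk days, with an assumed 2 to 7 such days a week, uses 0.64 × 2 × 4 = 5.1 to 0.64 × 7 × 4 = 17.9 of 28 tablets, leaving about 10 to 23. The documents do not support that. The number of high-risk days is assumed, full carry-over is assumed although 8.3 lists dispensing among weekly-visit activities, and EMI is meant to raise dosing above the pilot's level: at an assumed 90% on seven days a week, 28 − 25.2 = 2.8 would remain.

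**Conclusion.** The concern holds in this form: the reminder rule in 8.9, as written, works against the withholding and removal rules in 13.3, because it takes no account of study-drug status. This is more than a missing detail, since following one stated rule literally undercuts another that exists for safety.

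Its size is bounded, not known: up to 56 days of possible prompting after a week-4 positive, 28 after week 8 and none after week 12, on the assumptions that EMA follow-up continues and that withholding lasts to the end of treatment. The share of participants who will be off drug is not given, and the number of tablets they hold cannot be derived.

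Three stronger conclusions may be tempting and are not supported. Continued follow-up of opioid or fentanyl positives is not stated. Removal for intolerance is not automatic. And the effect on data is confined to EMI process measures and an exploratory analysis; nothing here shows that the primary urine comparison or the estimates for Aims 2 and 3 would change.

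**What to change.** Reconcile 8.9 (Study medication; EMA and EMI procedures) with 13.3.

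1. In 8.9, make the trigger take account of study-drug status, so that the text says what the platform does while 13.3 has a participant off drug.
2. In 13.3, state whether withholding covers tablets already dispensed or only new supply, and whether participants with a positive test remain in EMA follow-up.
3. In 8.13 and the SAP, report EMI receipt and the exploratory pathway from EMA to prompt to pill with on-drug and off-drug days distinguished. Showing both is preferable to dropping the off-drug days, because being off drug is a post-randomization event.

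What the clinical rule should be, including whether and when drug is resumed, is for the sponsor's clinicians.

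The cost is one status flag in the platform and a few sentences, with no additional participants, visits or tests. The drawback is that staff must keep the flag current: an outdated flag would send or suppress reminders wrongly and would misclassify days in the analysis.
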